Step 4	The null hypothesis for the third secondary endpoint is that there is no treatment difference in change from baseline to Week 24 in post-Valsalva LVOT-G in the FAS. The hypotheses will be tested at the two-sided significance level of 0.05. If this hypothesis is rejected, testing will proceed to Step 5; otherwise testing will stop.
Step 5	The null hypothesis for the fourth secondary endpoint is that there is no treatment difference in the proportion of patients with post-Valsalva LVOT-G < 30 mmHg at Week 24 in the FAS. The hypotheses will be tested at the two-sided significance level of 0.05. If this hypothesis is rejected, testing will proceed to Step 6; otherwise testing will stop.
Step 6	The null hypothesis for the fifth secondary endpoint is that there is no treatment difference in duration for SRT eligible during the 24-Week treatment period in patients who were SRT eligible at baseline in the FAS. The hypothesis will be tested at the two-sided significance level of 0.05. If this hypothesis is rejected, testing will proceed to Step 7; otherwise testing will stop.
Step 7	The null hypothesis for the sixth secondary endpoint is that there is no treatment difference in the change from baseline to Week 12 in KCCQ-CSS in the FAS. The hypothesis will be tested at the two-sided significance level of 0.05. If this hypothesis is rejected, testing will proceed to Step 8; otherwise testing will stop.
Step 8	The null hypothesis for the seventh secondary endpoint is that there is no treatment difference in proportion of patients with ≥ 1 NYHA functional class improvement at Week 12 in the FAS. The hypotheses will be tested at the two-sided significance level of 0.05. If this hypothesis is rejected, testing will proceed to Step 9; otherwise testing will stop.
Step 9	The null hypothesis for the eighth secondary endpoint is that there is no treatment difference in change from baseline to Week 12 in post-Valsalva LVOT-G in the FAS. The hypotheses will be tested at the two-sided significance level of 0.05. If this hypothesis is rejected, testing will proceed to Step 10; otherwise testing will stop.

Step 10	The null hypothesis for the ninth secondary endpoint is that there is no treatment difference in the proportion of patients with post-Valsalva LVOT-G < 30 mmHg at Week 12 in the FAS. The hypotheses will be tested at the two-sided significance level of 0.05. If this hypothesis is rejected, testing will proceed to Step 11; otherwise testing will stop.

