For the proportion of patients with ≥ 1 class improvement in NYHA class at Week 12, Week 16 NYHA class will be used if Week 12 NYHA class is not available. Week 8 NYHA class will be used if Week 16 NYHA is not available. Patient will be considered as not achieving ≥ 1 improvement in NYHA class at Week 12 if no NYHA at Weeks 8, 12 and 16 is available. Similarly, Week 20 NYHA class will be used if Week 24 NYHA is not available. Patient will be considered as not achieving ≥ 1 improvement in NYHA class at Week 24 if Week 20 and Week 24 NYHA are not available. A sensitivity analysis will be performed by repeating Cochran–Mantel–Haenszel (CMH) test by assigning missing NYHA class at Weeks 12 and 24 as non-responders. Proportion of patients with ≥ 1 class improvement in NYHA class will be analyzed using CMH test stratified by randomization factors. The p-value and 95% CI will be obtained using exact method.

Subgroup analysis will be done by repeating the CMH test for each subgroup level without specifying stratifying by randomization stratification factors.

4. Proportion of patients with post-Valsalva LVOT-G < 30 mmHg at Weeks 12 and 24

For the proportion of patients with post-Valsalva LVOT < 30 mmHg at Week 12, Week 16 post-Valsalva LVOT will be used if Week 12 visit is performed but post Valsalva LVOT is not available. Week 8 post-Valsalva LVOT will be used if Week 16 is not available. Similarly, Week 20 post Valsalva LVOT will be used if Week 24 is performed but post Valsalva LVOT is not available.

Proportion of patients with post-Valsalva LVOT-G < 30 mmHg at Weeks 12 and 24 will be analyzed using Cochran–Mantel–Haenszel (CMH) test stratified by randomization factors. The p-value and 95% CI will be obtained using exact method.

Subgroup analysis will be done by repeating the CMH test for each subgroup level without specifying stratifying by randomization stratification factors.

- Total duration of SRT eligibility during the 24-Week treatment period in patients who were SRT eligible at baseline

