Patient SRT eligibility will be assigned after data handling in case there are missing NYHA class or LVOT assessments. Intermittent missing NYHA or LVOT will be imputed follows the same imputing method for missing Week 12 or Week 24; e.g., impute Week 16 NYHA if Week 20 NYHA is available or use Week 12 NYHA if Week 20 NYHA is not available. Patient will be treated as SRT eligible if SRT eligibility can't be determined due to the missing NYHA class or LVOT assessments or clinical visits not performed after patient early terminates from the study.

Total duration will be calculated as the number of days patients are SRT eligible, from the date of the randomization until Week 24. Total duration will be 24 weeks if a patient remains SRT eligible at all visits from baseline until Week 24 (regardless of whether a patient is SRT eligible at Week 24 or not). Because the SRT eligibility status of a patient may change during the study conduct, only intervals during which the patient is SRT eligible, will be summed. The start of the interval is the time of randomization (or resumption of SRT eligible status), and the end of the interval is the date prior to the visit when the patient becomes SRT not eligible.

SRT (Y/N) Case #	Week 2	Week 4	Week 6	Week 8	Week 12	Week 16	Week 20	Week 24	Duration SRT Eligible (Weeks)
1	N	Y	Y	Y	N	N	Y	Y	12
2	Y	Y	N	N	Y	N	N	Y	10
3	Y	Y	N	N	N	N	N	N	6
4	Y	Y	N	N	Y	N	Y	N	14
5	Y	Y	N	N	Y	N	Y	Y	14

Total duration of SRT eligibility during the 24 Week of treatment period will be analyzed using an ANCOVA model includes treatment and randomization stratification factor beta blocker use/non-use as fixed effects and significant baseline characteristics as covariates. Stepwise model selection method will be used based on the default stay or entry level of 0.05 to evaluate significant baseline covariates. Sensitivity analysis of the SRT eligible endpoints includes repeating the same ANCOVA analysis the area under the curve calculated using the numeric value assigned to the SRT eligibility at each visit and treatment duration until Week 24, where SRT eligibility is assigned to value of 1 and SRT not eligible is assigned to value of 0.

- Change in total workload during CPET from baseline to Week 24

The primary and sensitivity analysis for the total workload will follow the same analysis approach for the primary estimand of the primary endpoint.

Subgroup analysis will be performed similarly as specified for the primary endpoint.

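### The rule for total duration of SRT eligibility and its worked example disagree: Case 1 is 14 weeks under the text of SAP 7.8.1, but the table prints 12

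*SAP*

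**What the plan says.** The endpoint is "Total duration of SRT eligibility during the 24-Week treatment period in patients who were SRT eligible at baseline". SAP Section 7.8.1 sets out the derivation:

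- Counting period: "Total duration will be calculated as the number of days patients are SRT eligible, from the date of the randomization until Week 24".
- Which time counts: "only intervals during which the patient is SRT eligible, will be summed".
- Interval limits: "The start of the interval is the time of randomization (or resumption of SRT eligible status), and the end of the interval is the date" before the first visit without eligibility. In full, "the end of the interval is the date prior to the visit when the patient becomes SRT not eligible".
- A patient eligible at every visit scores 24 weeks, "regardless of whether a patient is SRT eligible at Week 24 or not".

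A table of five cases follows. It gives eligibility (Y/N) at Weeks 2, 4, 6, 8, 12, 16, 20 and 24 and a total in weeks. It has no baseline column. The printed totals for Cases 1 to 5 are 12, 10, 6, 14 and 14.

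Section 7.6, Table 4, tests this endpoint at Step 6. The null hypothesis is "no treatment difference in duration for SRT eligible during the 24-Week treatment period in patients who were SRT eligible at baseline in the FAS". If it is not rejected, Steps 7 to 11 are not tested.

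**The concern.** The text and the table sit together and are the only specification of this derivation. Protocol Sections 9.4.1.1 and 9.4.3 define SRT eligibility but give no rule for counting intervals, and the sample code in SAP Section 11.5 has none for this endpoint.

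Case 1 is the only case not eligible at Week 2, so it is the only row that shows how the time from randomization to Week 2 is counted. It is also the row that contradicts the text. Code written from the text would fail a check against Case 1. Code that gives the first two weeks the Week 2 status would pass all five examples, yet would credit every patient not eligible at Week 2 with two weeks less than the text requires. If the arms differ in the share of patients who lose eligibility by Week 2, the choice moves the treatment difference at a confirmatory step.

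**Working it through.** **Inputs.** The visit grid, statuses and printed totals come from the SAP 7.8.1 table. Status at Week 0 is Y for every case, because the endpoint is restricted to patients eligible at baseline. SAP 5.6 takes baseline as the last measurement before the first dose, and Protocol Section 5 places randomization before that dose on Day 1.

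**Formula.** With visits at Weeks 0, 2, 4, 6, 8, 12, 16, 20 and 24, each interval takes the status at its start, and total duration is the sum of the lengths of the eligible intervals. Week 24 status adds no time, as the text says.

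| Case | Weeks 2, 4, 6, 8, 12, 16, 20, 24 | Text rule | Printed |
|---|---|---|---|
| 1 | N Y Y Y N N Y Y | (0–2) 2 + (4–12) 8 + (20–24) 4 = **14** | **12** |
| 2 | Y Y N N Y N N Y | (0–6) 6 + (12–16) 4 = 10 | 10 |
| 3 | Y Y N N N N N N | (0–6) 6 = 6 | 6 |
| 4 | Y Y N N Y N Y N | 6 + 4 + (20–24) 4 = 14 | 14 |
| 5 | Y Y N N Y N Y Y | 6 + 4 + 4 = 14 | 14 |

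Four rows reproduce. Case 1 misses by exactly the interval from randomization to Week 2. Counting in days on the scheduled visit days gives 98 days for Case 1, and 98 / 7 = 14 weeks.

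**Can another reading give 12 for Case 1?**

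- Carrying each status backward: 14. Trapezoidal area: 14. Eligible at both ends of an interval: 8. Eligible at either end: 20. None gives 12.
- Dropping randomization to Week 2 for everyone: 12, 8, 4, 12, 12. This fits Case 1 and breaks the other four.
- Giving randomization to Week 2 the Week 2 status, then carrying forward: 12, 10, 6, 14, 14. This fits all five, and also the 24 weeks for a patient eligible throughout, but it contradicts the written start at randomization.
- Taking Case 1 as not eligible at baseline: 12, but such a patient is outside the endpoint's population.
- One mistyped status in Case 1, text rule kept: changing Week 2 gives 16, Week 4 gives 12, Week 6 gives 12, Week 8 gives 10, Week 12 gives 18, Week 16 gives 18, Week 20 gives 10 and Week 24 gives 14. An error at Week 4 or Week 6 would therefore explain the printed 12.

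**Size of the difference.** Compare the text rule with the rule that fits all five rows. Eight visits give 2^8 = 256 status patterns. The rules differ by 2 weeks for the 128 with N at Week 2 and by 0 for the other 128. A patient not eligible at any visit scores 2 weeks under the text and 0 under the other rule.

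Let p_A and p_P be the proportions not eligible at Week 2 on aficamten and placebo. Moving from the text rule to the other rule changes the unadjusted mean difference (aficamten minus placebo) by −2 × (p_A − p_P) weeks. A shorter duration is favourable, so a negative change favours aficamten. The documents give no value for p_A or p_P, so the differences below are assumptions:

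| Assumed p_A − p_P | Change in mean difference (weeks) |
|---|---|
| −10 points | −2 × (−0.10) = +0.2, toward placebo |
| 0 | 0 |
| +20 points | −2 × 0.20 = −0.4, toward aficamten |
| +40 points | −2 × 0.40 = −0.8, toward aficamten |

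Moving from the other rule to the text reverses each sign.

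**The case against.** The strongest reply is that the text is explicit and the table only illustrates it. For a patient eligible at baseline, the sentence on interval limits leaves no doubt that the first two weeks count, and four of the five examples agree. The alternative rule appears nowhere in the documents, and a slip in one cell explains the table just as well. Anyone coding from the text would get 14 and notice the mismatch. The SAP also plans an area-under-the-curve sensitivity analysis built from visit statuses. Finally, every aficamten patient is still on the starting dose up to Week 2, so a 40-point difference at that visit has no support in the documents.

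Much of this stands. The text is the better guide to what was meant, the larger assumed differences are illustrations only, and no effect on the Step 6 conclusion has been shown. The 2 weeks is also nominal: the SAP counts days, and the Week 2 visit has a +3 day window. But none of this removes the contradiction. A worked example belongs to the specification, and this one fits a coherent rule other than the written one. The sensitivity analysis does not settle how the tested endpoint is derived.

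**Conclusion.** The inconsistency is real: 14 weeks under the text against 12 printed for Case 1, with Cases 2 to 5 in agreement. This rests on baseline eligibility, which the endpoint's population guarantees. The documents do not show whether the total is wrong, a status is mistyped, or a different rule was intended.

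The stake is a nominal 2 of 24 weeks for each patient not eligible at Week 2. The direction and size of any shift in the treatment comparison are unknown, because neither document gives eligibility rates at Week 2. The point should be fixed because it concerns the derivation of a multiplicity-controlled endpoint, and a failure at Step 6 would close the remaining steps.

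**What to change.** Before database lock, reconcile the text and Case 1 in SAP Section 7.8.1:

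- State that the written interval rule governs, and that the time from randomization to Week 2 counts as eligible for every patient in this analysis. This follows the explicit sentence, the baseline-eligible population and four of the five examples.
- Print 14 weeks for Case 1 with the statuses shown or, if a status was mistyped, correct that cell instead.
- Add a baseline column to the table, Y for all five cases.

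The cost is one sentence, one table cell and one table column. Data collection does not change.

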9.4.3. Secondary Endpoint(s)

The secondary endpoint(s) of the study are:

- Change in KCCQ-CSS from baseline to Week 12 and Week 24
- Proportion of patients with ≥ 1 class improvement in NYHA Functional Class from baseline to Week 12 and Week 24
- Change in post-Valsalva LVOT-G from baseline to Week 12 and Week 24
- Proportion of patients with post-Valsalva LVOT-G < 30 mmHg at Week 12 and Week 24
- Duration of eligibility for septal reduction therapy (SRT) during the 24-week treatment period in patients who were eligible for SRT at baseline. Participants are classified as being SRT eligible if they have NYHA Class ≥ 3 AND resting or Valsalva LVOT-G ≥ 50 mmHg.
- Change in total workload during CPET from baseline to Week 24

Change in KCCQ-CSS and change in post-Valsalva LVOT-G from baseline to Week 12 and Week 24 will be analyzed using a mixed model repeated measures (MMRM) model with baseline as covariate, randomization stratification factors, visit, treatment group, and interaction terms of treatment by visit and baseline by visit. An unstructured covariance matrix will be specified.

Proportion of patients with ≥ 1 class improvement in NYHA Functional Class from baseline to Week 12 and Week 24 or proportion of patients with post-Valsalva LVOT-G < 30 mmHg at Week 12 and Week 24 will be analyzed using Cochran–Mantel–Haenszel (CMH) test stratified by randomization factors. Patient's Week 20 NYHA Functional Class will be used when Week 24 NYHA Functional Class is not available. Total duration of SRT eligibility (NYHA Class ≥ 3 AND resting or Valsalva LVOT-G ≥ 50 mmHg) during the 24-week treatment period will be analyzed using an ANCOVA model with treatment group and randomization stratification factor beta blocker use/no use as fixed effects adjusting for significant baseline characteristics. The p-value and 95% CI will be obtained using exact method. Adjustment of multiplicity of the primary and secondary endpoints is specified in [Section 9.4.1.1](#).

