3.4. Randomization

All eligible patients will be centrally assigned to randomized IP using the IWRS. Randomization will be stratified by use of beta-blockers (yes or no) and CPET exercise modality (treadmill or bicycle) and implemented in the IWRS.

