Total duration of SRT eligible during the 24-week of treatment period	Total duration of SRT eligible during the 24-week of treatment period will be analyzed using an ANCOVA model includes treatment and randomization stratification factor beta blocker use/non-use as fixed effects and significant baseline characteristics as covariates. Stepwise model selection method will be used based on the default stay or entry level of 0.05 to evaluate significant baseline covariates.	SRT eligible will be assigned value of 1 and SRT not eligible will be assigned value of 0. Area under the curve using the numeric value assigned and treatment duration until Week 24 will be calculated. AUC will be analyzed using the same ANCOVA model. Same ANCOVA model will be used to analyze the total time for SRT eligibility.	
Change in total workload during CPET from baseline to Week 24	Missing data will be imputed using multiple imputation method (Section 7.7.1). Complete dataset will be analyzed using an ANCOVA model with fixed effects of treatment, randomization stratification factors baseline total workload value and baseline body weight.	Sensitivity analysis 
 • ANCOVA model will be repeated with missing data from subjects who discontinued aficamten treatment as if the aficamten subjects were in the placebo arm. • Tipping point analysis Subgroup analyses for variables in Section 7.5	

¹See [Table 5](#) for details on the two estimands for the primary endpoint.

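### The Step 6 ANCOVA for SRT-eligibility duration prespecifies only one of the two randomization stratification factors and leaves CPET modality to stepwise selection

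*SAP*

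**What the plan says.** SAP 3.4 sets out the randomization: "Randomization will be stratified by use of beta-blockers (yes or no) and CPET exercise modality (treadmill or bicycle) and implemented in the IWRS".

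Step 6 is a confirmatory test. SAP 7.6, Table 4 begins its entry with "The null hypothesis for the fifth secondary endpoint is that there is no treatment difference in duration for SRT eligible", sets the level at two-sided 0.05, and stops testing if the hypothesis is not rejected. It applies only to patients who were SRT eligible at baseline.

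For this endpoint SAP 7.8.1 specifies: "ANCOVA model includes treatment and randomization stratification factor beta blocker use/non-use as fixed effects". Other covariates are chosen from the data: "Stepwise model selection method will be used based on the default stay or entry level of 0.05 to evaluate significant baseline covariates". SAP Table 6 repeats this, and the SAP synopsis gives the same beta-blocker-only model. Protocol 9.4.3 agrees: "ANCOVA model with treatment group and randomization stratification factor beta blocker use/no use as fixed effects adjusting for significant baseline characteristics". So does the protocol synopsis. None of these places mentions CPET modality for Step 6, lists the candidate covariates, or says why one stratification factor is fixed and the other is not. SAP 11.5 has no sample code for this ANCOVA.

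**The concern.** A factor used to stratify randomization is normally a fixed term in the analysis. If it is prognostic and left out, the model counts variation that the design has already balanced as noise, and the standard error is too large. In Step 6 one factor is fixed, and whether the other enters depends on the trial data.

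Step 6 makes this worth noticing. It uses a subset of the full analysis set, so it has fewer patients than the other steps. SRT eligibility is not itself a stratification factor, so modality is only approximately balanced between arms within the subset. Failure at Step 6 also stops the five tests at Steps 7 to 11.

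**Working it through.** **1. Compare the eleven confirmatory models.**

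| Steps | Analysis | Where | Factors carried |
|---|---|---|---|
| 1 | ANCOVA, pVO2 | SAP 7.7.1; code in 11.5 | both |
| 2, 4, 7, 9 | MMRM, KCCQ-CSS and Valsalva gradient | SAP 7.8.1; code in 11.5 | both |
| 3, 5, 8, 10 | CMH, NYHA response and gradient below 30 mmHg | SAP 7.8.1; code in 11.5 | both |
| 6 | ANCOVA, SRT-eligibility duration | SAP 7.8.1, Table 6; protocol 9.4.3 | beta-blocker use only |
| 11 | ANCOVA, total workload (follows the primary analysis) | SAP 7.8.1, Table 6 | both |

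Count: 1 + 4 + 4 + 1 = 10 tests with both factors, and one without.

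**2. The plan's own power figure (context only).** SAP 3.3.1 gives a difference of 1.5, SD 3.5, 135 per arm and 10% missing, so 135 × 0.9 = 121.5 per arm. Then 1.5 / (3.5 × √(2/121.5)) = 3.34, and power ≈ Φ(3.34 − 1.96) = 91.6%. This reproduces the stated figure of more than 90%. It belongs to Step 1. The documents give no sample size or power for Step 6 and no expected share of SRT-eligible patients.

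**3. Upper limit on the loss of precision if modality never enters.** If modality explains a share R² of within-arm variance, the standard error without it, relative to the standard error with it, is about 1/√(1 − R²). The R² values are assumed:
- 0.02: 1/√0.98 = 1.010
- 0.05: 1/√0.95 = 1.026
- 0.10: 1/√0.90 = 1.054

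The formula ignores the degree of freedom that the extra term uses, so it slightly overstates the loss.

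**4. Simulation with modality always omitted or always fixed.** All inputs are assumed: 270 patients; blocks within the four strata; 70% on beta-blockers; 50% on bicycle; a normally distributed outcome; 6,000 runs under the null and 3,000 under the alternative. The treatment effect was 0.6 SD with 25% eligible (0.25 × 270 ≈ 68 patients) and 0.35 SD with 100% eligible. A modality effect of 0.3 SD corresponds to R² ≈ 0.0225/1.0225 = 2.2%, and 0.6 SD to 0.09/1.09 = 8.3%.

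| Eligible share | Modality effect | Type I error, omitted / fixed | Power, omitted / fixed |
|---|---|---|---|
| 25% | 0 | 0.047 / 0.047 | 68.3% / 67.6% |
| 25% | 0.3 SD | 0.053 / 0.054 | 64.8% / 65.2% |
| 25% | 0.6 SD | 0.047 / 0.046 | 62.7% / 65.8% |
| 100% | 0 | 0.050 / 0.050 | 81.4% / 81.3% |
| 100% | 0.3 SD | 0.047 / 0.049 | 80.8% / 81.1% |
| 100% | 0.6 SD | 0.042 / 0.048 | 80.5% / 83.2% |

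The simulation error of a type I estimate is √(0.05 × 0.95/6000) ≈ 0.003. Omission does not inflate type I error, and it is slightly conservative when modality is strongly prognostic. It costs at most about 3 points of power. Fixing modality when it has no effect costs less than 1 point.

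**5. Simulation of the rule closer to the plan, with modality eligible for stepwise entry at 0.05.** Assumptions: 25% eligible, 45% bicycle, 65% on beta-blockers, modality the only candidate, treatment effect 0.68 SD, 4,000 runs per case.

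| Modality R² | Runs in which modality is selected | SE, stepwise ÷ fixed | Power, stepwise / fixed |
|---|---|---|---|
| 0.02 | about 20% | 0.996 | 75.9% / 75.3% |
| 0.05 | about 44% | 0.999 | 77.5% / 77.8% |
| 0.10 | about 75% | 1.001 | 77.4% / 77.3% |

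Type I error under the stepwise rule was 0.043 to 0.050. If modality can be selected, the loss is about zero.

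**The case against.** The strongest reply is that the planned model largely looks after itself. SAP 7.4 counts the stratification factors among the baseline covariates, and SAP 7.5 lists modality as a subgroup variable, so it is a natural stepwise candidate. The last table shows that, if it is a candidate, almost nothing is lost. This stands as an answer on precision. It does not settle prespecification: the text neither guarantees nor excludes modality as a candidate, and at R² = 0.02 it was selected in only about a fifth of runs.

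Second, beta-blocker use alone also appears in the exploratory SRT logistic model and its supporting CMH test (SAP 7.9.1) and in the stratified logistic code (SAP 11.5). That stands: it looks like a consistent choice for the SRT analyses. A reader might infer a conflict between protocol and SAP, but the two agree. What is missing is the reason. Sparse strata would be a possible one, but the documents do not give it, and an additive main effect needs no crossed cells.

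Third, nothing shows that modality is prognostic for this endpoint. The SRT definition contains no CPET measure, and the gradients analysed are core-laboratory values. A reader might infer that modality stands for site or country differences in NYHA grading, because protocol 8.2.1 allows cycle testing at laboratories that do not perform treadmill tests. The documents do not support that step: nothing links modality to country or to how NYHA class is graded.

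Fourth, a prespecified covariate list for Step 6 would settle modality as well. That is true, provided the list names it as a fixed term.

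**Conclusion.** The point holds as a minor one. Step 6 is the only confirmatory test that does not prespecify both randomization stratification factors, and no reason is given. The cost lies between about zero, if stepwise selection can bring modality in, and about 0 to 3 points of power, if it never enters and explains up to about 10% of within-arm variance. A reader might take the 1% to 5.4% increase in standard error as the expected loss. It is an upper limit for the case in which modality is never selected. Nor does the omission make the Step 6 test invalid, since type I error is not inflated.

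These sizes rest on assumed eligible shares, modality effects and treatment effects, and on a normally distributed outcome, whereas the real duration is bounded by the 24-week period. The stepwise simulation had one candidate, so it says nothing about selection from a longer, unlisted set. No figure stated in the documents changes.

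**What to change.** Name beta-blocker use and CPET modality as fixed effects in the Step 6 ANCOVA and in its AUC sensitivity version, and keep both outside the stepwise step. Align the five places that describe the model: the protocol synopsis, protocol 9.4.3, the SAP synopsis, SAP 7.8.1 and SAP Table 6. Make the exploratory SRT analyses in SAP 7.9.1 and the stratified logistic code in SAP 11.5 consistent with them. Make the change before unblinding, which SAP 4.2 places after database lock.

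The cost is a few words in each place and one degree of freedom (with about 68 patients, and before any selected covariates, 65 residual degrees of freedom become 64). If modality turns out not to be prognostic, up to about 1 point of power is lost.
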